3.1.1 Administrative structure of the trial

The trial is sponsored by Boehringer Ingelheim (BI) Pharma GmbH & Co. KG, Germany.

BI has appointed a Trial Clinical Monitor, responsible for coordinating all required activities, in order to

- manage the trial in accordance with applicable regulations and internal SOPs,
- direct the clinical trial team in the preparation, conduct, and reporting of the trial,
- ensure appropriate training and information of local clinical monitors (CML), Clinical Research Associates (CRAs), and participating trial sites.

The trial medication will be provided by the Clinical Trial Supplies Unit (CTSU), BI Pharma GmbH & Co. KG, Biberach, Germany.

The trial will be conducted at the Human Pharmacology Centre (HPC) of BI Pharma GmbH & Co. KG, Biberach, Germany, under the supervision of the Principal Investigator.

Safety laboratory tests will be performed by the local laboratory of the trial site (

The analyses of BI 894416 concentrations in plasma will be performed at

The digitally recorded 12-lead ECGs will be sent to a specialised contract research organisation () for evaluation.

On-site monitoring will be performed by BI or a contract research organisation appointed by BI.

Data management and statistical evaluation will be done by BI according to BI SOPs.

Tasks and functions assigned in order to organise, manage, and evaluate the trial are defined according to BI SOPs. A list of responsible persons and relevant local information can be found in the ISF.

3.2 DISCUSSION OF TRIAL DESIGN, INCLUDING THE CHOICE OF CONTROL GROUP

For single-rising dose trials, the design described in [Section 3.1](#) is viewed favourable under the provision not to expose the subjects involved to undue risks since the main study objective is to investigate safety and tolerability of BI 894416.

With the rising dose design, single-blind conditions regarding the subject's treatment (active or placebo) are maintained within each dose group. However, the current dose level will be known to subjects and investigators. The disadvantage of this trial design is a possible observer bias with regard to the dose-depending effects as well as time effects, but it has the virtue of minimizing subject risk by sequentially studying ascending doses. As time effects are expected to be small relative to the differences between the doses in the range investigated, unbiased comparisons between treatments can still be expected.

It is standard in trials involving healthy volunteers to include a placebo group as control for the evaluation of safety, tolerability and pharmacodynamic effects. Each dose group consists of 8 subjects with 6 on active treatment, and 2 on placebo. The placebo control group includes all subjects of all dose groups treated with placebo. 6 subjects per active treatment group are in general considered as sufficient for the exploratory evaluation of pharmacokinetics.

For the rel BA part, that is designed to assess relative bioavailability of tablet vs. oral solution formulation at a dose of 10 mg BI 894416 and to obtain pharmacokinetic data at a dose of 40 mg BI 894416 as tablet formulation, the crossover design is viewed favourable due to its efficiency: since each subject serves as his own control, the comparison between the treatments is based on a comparison within subjects rather than between subjects. Thus the inter-subject variability is removed from the comparison between treatments [[R94-1529](#)]. The first two periods that compare 10 mg oral solution with 10 mg tablet follow a two-way randomized crossover design, and the third treatment period, 40 mg BI 894416 as tablets, follows in a fixed-sequence crossover design. Subjects will only be treated in the third treatment period if allowed after analysis of preliminary PK and safety data of the preceding periods. This design is chosen to ensure that gMean plasma exposure values of BI 894416 in terms of C_{max} and AUC_{0-24} in the rel BA part do not exceed gMean plasma exposure values in terms of C_{max} and AUC_{0-24} that were observed previously in the SRD part of the trial and that were associated with acceptable safety and tolerability. Treatments in the rel BA part are open-label, as treatments are distinguishable and PK parameters are not expected to be influenced by knowledge of treatment.

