4.1.5 Blinding and procedures for unblinding

4.1.5.1 Blinding

The treatments administered in the SRD part (active or placebo) will be single-blind (that is, subjects will not know whether they receive active treatment or placebo). However, the current dose level will be known to the subjects. Treatments of the rel BA part will be open-label because the treatments are distinguishable from each other, and because knowledge of treatment is not expected to influence PK parameters.

For SRD part: Within the central ECG lab, the staff involved with interval measurements will be blinded with respect to the treatment and also with regard to the recording date and time as well as planned time points of the ECGs. The interval measurements for a given subject will be performed in a random and blinded sequence by a single technician.

For SRD part: If an interim safety analysis of ECG data is required, a part of the staff of the central ECG lab may be unblinded. This part of the staff will be strictly separated from the blinded staff members who are involved with ECG interval measurements and assessments of ECGs.

Furthermore, the trial bioanalyst, the trial biomarker analyst, the drug metabolism scientist and trial pharmacokineticist may receive the randomisation codes to perform the preliminary PK analysis. He or she will confirm in writing that the codes will be treated confidentially.

The database of this trial will be handled open-label, because no bias with regard to data cleaning of safety measures is expected.

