4.1.5.2 Procedures for emergency unblinding

As this trial will be conducted single-blind in the SRD part and open-label in the rel BA part, the treatment information will be known to the investigator (SRD part) or to both investigator and subjects (rel BA part). Therefore, no emergency envelopes will be provided.

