5.2 SAFETY

5.2.1 Endpoints of safety

SRD part

Primary endpoint to assess safety and tolerability of BI 894416 is the number [N (%)] of subjects with drug-related adverse events.

Rel BA part

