The definition of an adverse reaction (i.e., a drug-related adverse event) implies at least a reasonable possibility of a causal relationship between a suspected medicinal product and an adverse event. An adverse reaction, in contrast to an adverse event, is characterised by the fact that a causal relationship between a medicinal product and an occurrence is suspected.

Medical judgment should be used to determine the relationship, considering all relevant factors, including pattern of reaction, temporal relationship, de-challenge or re-challenge, confounding factors such as concomitant medication, concomitant diseases and relevant history.

Arguments that may suggest that there is a reasonable possibility of a causal relationship could be:

- The event is consistent with the known pharmacology of the drug
- The event is known to be caused by or attributed to the drug class.
- A plausible time to onset of the event relative to the time of drug exposure.
- Evidence that the event is reproducible when the drug is re-introduced
- No medically sound alternative aetiologies that could explain the event (e.g. pre-existing or concomitant diseases, or co-medications).
- The event is typically drug-related and infrequent in the general population not exposed to drugs (e.g. Stevens-Johnson syndrome).
- An indication of dose-response (i.e. greater effect size if the dose is increased, smaller effect size if dose is diminished).

Arguments that may suggest that there is no reasonable possibility of a causal relationship could be:

- No plausible time to onset of the event relative to the time of drug exposure is evident (e.g. pre-treatment cases, diagnosis of cancer or chronic disease within days / weeks of drug administration; an allergic reaction weeks after discontinuation of the drug concerned)
- Continuation of the event despite the withdrawal of the medication, taking into account the pharmacological properties of the compound (e.g. after 5 half-lives). Of note, this criterion may not be applicable to events whose time course is prolonged despite removing the original trigger.
- Additional arguments amongst those stated before, like alternative explanation (e.g. situations where other drugs or underlying diseases appear to provide a more likely explanation for the observed event than the drug concerned).
- Disappearance of the event even though the study drug treatment continues or remains unchanged.

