The REP for BI 894416, when measurable drug levels or PD effects are still likely to be present after the last administration, is not known for this first-in-human trial. Therefore, all AEs reported until the end of trial examination (last per protocol contact) will be considered on treatment; please see [Section 7.3.3](#).

AE reporting to sponsor and timelines

The Investigator must report SAEs, AESIs, and non-serious AEs which are relevant for the reported SAE or AESI, on the BI SAE form via fax immediately (within 24 hours of awareness) to the sponsor's unique entry point (country specific contact details will be provided in the ISF). The same timeline applies if follow-up information becomes available. In specific occasions the Investigator could inform the sponsor upfront via telephone. This does not replace the requirement to complete and fax the BI SAE form.

With receipt of any further information to these events, a follow-up SAE form has to be provided. For follow-up information the same rules and timeline apply as for initial information.

Information required

For each AE, the investigator should provide the information requested on the appropriate CRF pages and the BI SAE form (if applicable). The investigator should determine the causal relationship to the trial medication.

The following should also be recorded as an (S)AE in the CRF and on the SAE form (if applicable):

- Worsening of the underlying disease or of other pre-existing conditions
- Changes in vital signs, ECG, physical examination, neurological examination and laboratory test results, if they are judged clinically relevant by the investigator.

If such abnormalities already pre-exist prior to trial inclusion they will be considered as baseline conditions and should be collected in the CRF only.

All (S)AEs, including those persisting after individual subject's end of trial must be followed up until they have resolved, have been sufficiently characterised, or no further information can be obtained.

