7. STATISTICAL METHODS AND DETERMINATION OF SAMPLE SIZE

7.1 STATISTICAL DESIGN – MODEL

7.1.1 Objectives

SRD part:

The primary objective of this trial is to investigate the safety and tolerability of BI 894416 by using descriptive statistics for all endpoints comparing active dose groups to placebo. The primary endpoint is defined in [Section 5.2.1](#). Inferential statistics is not planned (as explained in [Section 7.2](#)).

Secondary objectives are the exploration of pharmacokinetics (PK) of BI 894416. Endpoints as specified in [5.5.1](#) will be analysed by descriptive statistics.

Rel BA part

Secondary objective of the rel BA part is to investigate the pharmacokinetics of BI 894416 as tablet formulation and to explore the relative bioavailability of 10 mg of BI 894416 tablet formulation (Test, T) compared to 10 mg of BI 894416 oral solution formulation (Reference, R). The rel BA part is designed to allow intra-subject comparisons and will be evaluated statistically by use of an appropriate linear model in an exploratory fashion.

The assessment of safety and tolerability will be an additional objective of the rel BA part of this trial, and will be evaluated by descriptive statistics.

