7.3.3 Safety analyses

Safety will be assessed for the endpoints and parameters of interest listed in [Section 5.2.1](#). All treated subjects (that is, all subjects who received at least one dose of study drug), will be included in the safety analysis. Safety analyses will be descriptive in nature and will be based on BI standards. No hypothesis testing is planned.

Treatments will be compared in a descriptive way. For the SRD part, the placebo control group in the safety evaluation will consist of all placebo treated subjects, regardless of the dose group in which they were treated. Treatment groups will be compared in a descriptive way. Tabulations of frequencies/proportions will be used for the evaluation of categorical (qualitative) data, and tabulations of descriptive statistics will be used to analyse continuous (quantitative) data.

The analyses will be done by 'treatment at onset'.

Measurements (such as ECG, vital signs, or laboratory parameters) or AEs will be assigned to treatments (see [Section 4.1](#)) based on the actual treatment at the planned time of the measurement or on the recorded time of AE onset (concept of treatment emergent AEs). Therefore, measurements planned or AEs recorded prior to first intake of trial medication will be assigned to 'screening', those between trial medication intake in a period until trial medication intake in the next period or the trial termination date will be assigned to the treatment period. These assignments including the corresponding time intervals will be

defined in detail in the TSAP. Please note that AEs occurring after the last per protocol contact but entered before database lock will be reported to drug safety only and will not be captured in the trial database.

Additionally, further treatment intervals (analysing treatments) may be defined in order to provide summary statistics for time intervals, such as combined treatments, on-treatment totals or periods without treatment effects (such as screening and follow-up intervals).

Adverse events will be coded using the Medical Dictionary for Regulatory Activities (MedDRA). Frequency, intensity and causal relationship of AEs will be tabulated by treatment, system organ class and preferred term. SAEs, AESIs (see [Section 5.2.2.1](#)) and other significant AEs (according to ICH E3) will be listed separately.

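### Does an unblinded causality rating undermine the placebo comparison of drug-related adverse events enough to change the plan?

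*Protocol*

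**What the plan says.** Protocol 5.2.1 defines the SRD endpoint: "Primary endpoint to assess safety and tolerability of BI 894416 is the number [N (%)] of subjects with drug-related adverse events". Protocol 5.2.2.2 assigns the rating: "The investigator should determine the causal relationship to the trial medication". SAP 7.8.1 likewise builds the primary table from the investigator's judgement.

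The SRD part is single-blind. Under Protocol 4.1.5.1 the subjects do not know whether they receive active drug or placebo. Protocol 4.1.5.2 gives the other side: "the treatment information will be known to the investigator (SRD part").

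Protocol 7.1.1 sets the primary objective, to be met "by using descriptive statistics for all endpoints comparing active dose groups to placebo", and Protocol 7.3.3 specifies that "the placebo control group in the safety evaluation will consist of all placebo treated subjects". Protocol 7.2 and 7.3.3 exclude hypothesis testing.

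Protocol 3.2 discusses what the design costs. It names possible observer bias, in relation to dose and time, as the drawback and sets it against the lower risk of studying doses in ascending order. It then argues that time effects should be small compared with dose differences, so that "unbiased comparisons between treatments can still be expected".

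**The concern.** The rating that defines the primary endpoint is a medical judgement made by someone who knows the allocation. Some of the arguments for causality in Protocol 5.2.2.1 seem to need actual exposure to the drug, for example "A plausible time to onset of the event relative to the time of drug exposure", or agreement with its known pharmacology. An investigator who knows that a subject took placebo may be slower to call an event drug-related. The two columns of the primary table could then differ through rating alone, and a reader could take the difference for a tolerability signal.

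The statement in Protocol 3.2 seems to rule this out, but its reason concerns drift over calendar time and not knowledge of treatment. The plan does protect another measurement: "Within the central ECG lab, the staff involved with interval measurements will be blinded with respect to the treatment". The visible text describes nothing similar for causality.

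**Working it through.** **1. The factual chain.** Each link is in the current text: an endpoint that depends on judgement (Protocol 5.2.1, 5.2.2.1), a rater who knows the treatment (4.1.5.2, 5.2.2.2), and a descriptive comparison with pooled placebo (7.1.1, 7.3.3; SAP 6.1). The comparison is therefore open to assessment bias.

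**2. Head counts.** The protocol's totals reproduce: 8 groups × 8 = 64 SRD subjects and 64 + 12 = 76 in total; with ten groups, 10 × 8 = 80 and 80 + 12 = 92. Each group has 6 active and 2 placebo subjects (Protocol 3.1). If groups are full:

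- the seven SRD doses in SAP 6.1 give 7 × 6 = 42 active and 7 × 2 = 14 placebo subjects;
- the protocol's ten groups give 10 × 6 = 60 active and 10 × 2 = 20 placebo subjects.

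**3. Effect of one call that changes a subject's status.**

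- Pooled placebo: 1/14 = 7.1 percentage points, or 1/20 = 5.0 points with ten groups.
- One active dose group: 1/6 = 16.7 points.

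These are reciprocals of the group sizes. They show how coarse the table is and would be the same for any misclassification.

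**4. Illustration under assumptions.** Suppose the drug has no effect, so that the share *r* of subjects with any AE is equal in both arms. Let *a* and *b* be the shares of those subjects rated as having a drug-related AE on active and on placebo. The spurious excess is *r* × (*a* − *b*). The documents give none of these values.

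| Gap *a* − *b* | *r* = 20% | *r* = 40% |
|---|---|---|
| 0 | 0 points | 0 points |
| 10 points | 2 points | 4 points |
| 25 points | 5 points | 10 points |
| 50 points | 10 points | 20 points |

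At the largest gap the number of placebo subjects involved is 14 × 0.2 × 0.5 = 1.4 to 14 × 0.4 × 0.5 = 2.8. The range starts at zero, and nothing in the documents says where in it the trial would fall.

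**5. The direction.** Fewer related calls on placebo is plausible but not established. Protocol 5.2.2.2 asks for causality to the trial medication. Protocol 4.1.4 covers both active and placebo solutions in describing that medication, and SAP Table 6.1: 1 starts the placebo phase at administration of study drug. Time to onset and the absence of another explanation can be judged after a placebo dose too. Known pharmacology and drug class fit placebo less well.

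**6. What depends on the comparison.**

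- No test and no confirmatory claim (Protocol 7.2, 7.3.3).
- None of the stopping criteria in Protocol 3.3.4.2 compares active with placebo. The more-than-50% rule and the QT rule count actively treated subjects, and a single drug-related serious AE is enough on its own.
- SAP 7.8.1 tabulates subjects with any AE by treatment, and drug-related AEs separately, each also by maximum intensity. Protocol 7.3 has all individual data listed.

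The comparison that does not pass through the relatedness rating is therefore already planned.

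**The case for a change.** The best argument for a change is that it would be cheap and concerns the primary endpoint. Protocol 3.2 raises observer bias and then answers only the part about time, so its conclusion does not follow from its reason. A plan that blinds its ECG readers clearly knows what rater blinding is for. One could confine the sentence to time effects, add a caution to the drug-related placebo column, and let the placebo comparison rest mainly on all AEs.

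The gap in reasoning stands, but it is narrow. The sentence states its own condition about time effects and sits in a discussion of sequential dose groups, so it can fairly be read as limited to them. Protocol 4.1.5.2 is open about what the investigator knows. Confining the sentence would therefore mostly spell out a condition it already carries, and the caution is an interpretive remark for the report.

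Moving the weight to all AEs is the only part that would change the reading of the results, and it is not clearly better. Background events would dilute a true contrast. Unblinded medical staff also assess subjects for AEs (Protocol 5.2.2.2), and the investigator decides which laboratory, vital-sign and ECG findings count as AEs (SAP 7.8.2 to 7.8.4). Blinding of subjects protects their spontaneous reports only in part. Bias would be reduced by an unknown amount at the price of a less specific endpoint.

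**Conclusion.** No change to the plan is needed. The drug-related AE contrast with pooled placebo is open to assessment bias of unknown size and uncertain direction, and the reason in Protocol 3.2 does not exclude it. This is a disclosed limitation of a single-blind first-in-human design, accepted in a trade-off that the protocol sets out.

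One changed call is worth 7.1 points in a pooled placebo group of 14. The 0 to 20 points of spurious excess rest on assumed AE rates and rating gaps, with no drug effect. Neither figure bears on a test, a stopping criterion or a dose decision, because none of these uses the placebo contrast. An analyst who follows SAP 7.8.1 will produce both the any-AE and the drug-related tables, and a careful report will read them together and say that relatedness was rated unblinded.

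The conclusion rests on the visible text. Parts of Protocol 5.2 are not shown, so it cannot be said that no further safeguard exists. If one does, the concern weakens further.

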3.3 SELECTION OF TRIAL POPULATION

It is planned that 76 healthy male subjects will enter the study. The actual number of subjects entered may exceed the total of 76 if additional intermediate doses will be tested in the SRD part (see [Section 3.1](#)), but will not exceed 92 subjects entered. Subjects will be recruited from the volunteers' pool of the trial site.

A log of all subjects enrolled into the trial (i.e. having given informed consent) will be maintained in the ISF at the investigational site irrespective of whether they have been treated with investigational drug or not.

3.3.1 Main diagnosis for study entry

The study will be performed in healthy subjects.

3.3.2 Inclusion criteria

Subjects will only be included into the trial, if they meet the following criteria:

1. Healthy male subjects according to the assessment of the investigator, based on a complete medical history including a physical examination, vital signs (BP, PR), 12-lead ECG, and clinical laboratory tests
2. Age of 18 to 45 years (incl.)
3. BMI of 18.5 to 29.9 kg/m² (incl.)
4. Signed and dated written informed consent prior to admission to the study in accordance with GCP and local legislation

3.3.3 Exclusion criteria

Subjects will not be allowed to participate if any of the following general criteria apply:

1. Any finding in the medical examination (including BP, PR or ECG and including the neurological examination) is deviating from normal and judged as clinically relevant by the investigator
2. Repeated measurement of systolic blood pressure outside the range of 90 to 140 mmHg, diastolic blood pressure outside the range of 50 to 90 mmHg, or pulse rate outside the range of 50 to 90 bpm
3. Any laboratory value outside the reference range that the investigator considers to be of clinical relevance
4. Any evidence of a concomitant disease judged as clinically relevant by the investigator
5. Gastrointestinal, hepatic, renal, respiratory, cardiovascular, metabolic, immunological or hormonal disorders

Proprietary confidential information © 2018 Boehringer Ingelheim International GmbH or one or more of its affiliated companies

6. Cholecystectomy and/or surgery of the gastrointestinal tract that could interfere with the pharmacokinetics of the trial medication (except appendectomy and simple hernia repair)
7. Diseases of the central nervous system (including but not limited to any kind of seizures or stroke), and other relevant neurological or psychiatric disorders
8. History of relevant orthostatic hypotension, fainting spells, or blackouts
9. Chronic or relevant acute infections
10. History of relevant allergy or hypersensitivity (including allergy to the trial medication or its excipients)
11. Use of drugs within 30 days prior to administration of trial medication if that might reasonably influence the results of the trial (incl. QT/QTc interval prolongation)
12. Participation in another trial where an investigational drug has been administered within 60 days prior to planned administration of trial medication, or current participation in another trial involving administration of investigational drug
13. Smoker (more than 10 cigarettes or 3 cigars or 3 pipes per day);
14. Inability to refrain from smoking on specified trial days
15. Alcohol abuse (consumption of more than 30 g per day)
16. Drug abuse or positive drug screening
17. Blood donation of more than 100 mL within 30 days prior to administration of trial medication or intended donation during the trial
18. Intention to perform excessive physical activities within one week prior to administration of trial medication or during the trial
19. Inability to comply with dietary regimen of trial site
20. A marked baseline prolongation of QT/QTc interval (such as QTc intervals that are repeatedly greater than 450 ms) or any other relevant ECG finding at screening
21. A history of additional risk factors for Torsades de Pointes (such as heart failure, hypokalemia, or family history of Long QT Syndrome)
22. Subject is assessed as unsuitable for inclusion by the investigator, for instance, because considered not able to understand and comply with study requirements, or has a condition that would not allow safe participation in the study

In addition, the following trial-specific exclusion criteria apply:

23. History of relevant neurological disorder affecting the peripheral or central nervous system (this includes, but is not limited to: stroke, epilepsy, inflammatory or atrophic diseases affecting the nervous system, cluster headache or any cancer of the nervous system) *
24. History of immunological disease except allergy not relevant to the trial (such as mild hay fever or dust mite allergy) and except asthma in childhood or adolescence
25. History of cancer (other than successfully treated basal cell carcinoma)
26. Within 10 days prior to administration of trial medication, use of any drug that could reasonably inhibit platelet aggregation or coagulation (e.g., acetylsalicylic acid)

Proprietary confidential information © 2018 Boehringer Ingelheim International GmbH or one or more of its affiliated companies

27. Male subjects with WOCBP partner who are unwilling to use male contraception (condom or sexual abstinence) from time point of administration of trial medication until 30 days thereafter.

* Febrile seizures in childhood or adolescence, recovered carpal tunnel syndrome, recovered uncomplicated meningitis, recovered herpes zoster, tension headache, occasional benign tics (e.g. due to stress) or minor para- or dysesthesia (e.g. as a side effect of prior blood withdrawal) do not constitute a history of relevant neurological disorder.

For study restrictions, refer to [Section 4.2.2](#).

